## General Information

This document describes the PREVAIL trial and provides information about procedures for entering participants into it. The protocol should not be used as an aide-memoir or guide for the treatment of other patients; every care was taken in its drafting, but corrections or amendments may be necessary. These will be circulated to the registered investigators in the trial, but sites entering participants for the first time are advised to contact the coordinating centre Medicines for Children Clinical Trials Unit (MC CTU) to confirm they have the most up to date version. Clinical problems relating to this trial should be referred to the relevant Chief Investigator via the MC CTU.

This protocol defines the participant characteristics required for trial entry and the schedule of treatment and follow-up. Participant recruitment will be undertaken in compliance with this document and applicable regulatory and governance requirements and waivers to authorise non-compliance are not permitted. Incidence of protocol non-compliance, whether reported prospectively (e.g. where a treatment cannot be administered on a scheduled date as a result of public holidays) or retrospectively noted (e.g. as a result of central monitoring) are recorded as protocol deviations, the incidence of which are monitored and reported to trial oversight committees.

## Statement of Compliance

This trial will be carried out in accordance with the World Medical Association Declaration of Helsinki (1964) and the Tokyo (1975), Venice (1983), Hong Kong (1989) and South Africa (1996) amendments and will be conducted in compliance with the protocol, CTRC Standard Operating Procedures and EU Directive 2001/20/EC, transposed into UK law as the UK Statutory Instrument 2004 No 1031: Medicines for Human Use (Clinical Trials) Regulations 2004 as amended.

## Relationship Statements

The UK Clinical Research Collaboration (UKCRC; [www.ukcrc.org](http://www.ukcrc.org)) is a partnership organisation working to establish the UK as a world leader in clinical research. Following a review by an international panel, the Clinical Trials Research Centre (CTRC) at the University of Liverpool has been assessed as reaching the highest quality standard required by the UKCRC and achieved full UKCRC registration.

The CTRC encompasses clinical trials activity in areas including MC CTU), cancer (The Liverpool Cancer Trials Unit; LCTU), epilepsy, oral health and obstetrics and gynecology (<http://www.ctr.org.uk/>). All CTRC activities are underpinned by methodological rigour, a modern data management system, similar technical requirements and a common set of standard operating procedures.

The NIHR Clinical Research Network Children and National Cancer Research Network is part of the National Institute for Health Research Clinical Research Network.

## Glossary

AM-PICC	Antimicrobial Impregnated coated Peripherally Inserted Central Catheter
AE	Adverse Event
AI	Adverse Incident
AIC	Adverse Incident Centre
CCS	Continuing Care Site
CE	French phrase "Conformité Européene" which literally means "European Conformity". The symbol  is used by manufacturers to show that a medical device meets the relevant requirements of the regulations and that it is fit for its intended purpose.
CFU	Colony Forming Units
CHE	Centre for Health Economics - University of York
CI	Chief Investigator
CPA	Clinical Pathology Accreditation
CRF	Case Report Form
CTRC	Clinical Trials Research Centre
FR	French Gauge
GP	General Practitioner
HES	Hospital Episodes Statistics
HTA	Health Technology Assessment
ICH GCP	International Conference on Harmonisation Good Clinical Practice
IDSMC	Independent Data and Safety and Monitoring Committee
IMP	Investigational Medicinal Product
Kg	Kilograms
MHRA	Medicines and Healthcare products Regulatory Agency
NEC	Necrotising Enterocolitis
NRES	National Research Ethics Service
ONS	Office of National Statistics
PI	Principal Investigator
PICC	Peripherally Inserted Central Catheter
PREVAIL	Trial Title: PREVenting infection using Antimicrobial Impregnated Long lines – long lines will be referred to as PICCs throughout the protocol
MC CTU	Medicines for Children Clinical Trials Unit
MHRA	Medicines and Healthcare products Regulatory Agency
NNU	Neonatal Unit
NNRD	National Neonatal Research Database
R&D	Research & Development
RCT	Randomised Controlled Trial
REC	Research Ethics Committee
RN	Research Nurse – although the protocol refers to a RN it may be anyone who has been delegated the relevant duties on the delegation log.
S-PICC	Standard Peripherally Inserted Central Catheter
SAE	Serious Adverse Event
SOP	Standard Operating Procedure
TMG	Trial Management Group
TSC	Trial Steering Committee

# 1 PROTOCOL SUMMARY

Title:	PREVAIL: PREVenting infection using Antimicrobial Impregnated Long lines
Full Title:	An unblinded, 2-arm randomised controlled trial to determine the effectiveness and cost effectiveness of antimicrobial impregnated (with rifampicin and miconazole) long lines (termed peripherally inserted central venous catheters, or AM- PICC (AM-PICC)) compared with standard PICC (S-PICC) for reducing blood stream infection (BSI).
Part I:	Randomised controlled trial
Phase:	III
Population:	
The trial population aims to include 858 babies who require the narrowest PICC (Premicath 1 French gauge (Fr)). Premicaths are designed for babies <1kg and most participants will be very preterm (born at <32 weeks of gestation).
 
A PICC is usually inserted after the first 2 days of age to administer fluids, medicines and nutrition.

Trial Sites and Distribution:	The trial will take place in 18 Neonatal Units (NNUs) in England.
Trial Duration Recruitment: Follow up:	
2 years.
 
Participant follow-up to ascertain the primary outcome (BSI):
 
 
• 48 hours after removal of the randomised PICC or;
 
• 48 hours after attempted insertion of randomised PICC
 
 
Participant follow-up to ascertain secondary outcomes:
 
 
• Until discharge from NNU or;
 
• Death or;
 
• 6 months (26 weeks) post randomisation (whichever is sooner).
 
 
Data will be based on routinely recorded clinical data collated by the Research Nurse (RN).
 
For long-term participant follow-up please refer to part II.

Description of Agent/ Intervention:	We will use a web-based interface to randomly allocate new born babies to S-PICC or AM-PICC). All PICCs used in the trial are CE marked medical devices used for their intended purpose. AM-PICCs can be distinguished from S-PICCs as rifampicin causes brown staining on the tubing. Hence, this is an unblinded trial.
Primary Outcomes:	Time to BSI based on any positive blood/CSF culture . (any positive bacterial or fungal blood/CSF culture will be included) taken between 24 hours after randomisation until 48 hours after PICC removal.
Secondary Outcomes:	Secondary outcomes include: i) outcomes recorded during randomised PICC insertion: type of organisms isolated from BSI; evidence of rifampicin resistance in isolates from blood or PICC tips; other measures of BSI (rate of BSI per 1000 PICC days, rate of PICC related BSI per 1000 PICC days, occurrence of 1 or more BSI); rate of blood/CSF culture sampling per 1000 PICC days, duration of antimicrobial exposure; time to PICC removal ii) clinical outcomes recorded at discharge home from neonatal care: necrotising enterocolitis, chronic lung disease, retinopathy of prematurity, cranial ultrasound abnormalities, duration of parenteral nutrition, time to full milk feeds, death before discharge and within 6 months (26 weeks) of randomisation, time to death.

[figure not shown]
## **Part II Economic analysis**

Aim	To determine the cost-effectiveness of AM-PICC vs S-PICC to the NHS.
Objectives	To evaluate: 
 
i) The direct hospital costs of using AM-PICC compared with S-PICC up to 6 months from randomisation.
 
ii) The cost-effectiveness of AM-PICC compared with S-PICC over the participants' expected lifetime from the perspective of the NHS.
 
iii) The potential value of additional research to reduce any uncertainty observed in the cost-effectiveness model. This will be used to inform decisions about long-term follow up of the trial cohort.
 
iv) The value of implementing the cost-effective intervention (AM-PICC vs S-PICC) throughout the NHS in England and Wales.
 

v) The costs of a BSI to the NHS.

**Trial Duration:** Long term follow-up of participants from part I will be until 6 months after randomisation and will be ascertained from linked electronic records.

### 1.1 Schematic of Trial Design

## 2 BACKGROUND INFORMATION

### 2.1 Introduction

#### **Review of the literature and rationale for the trial:**

Preterm delivery is a major public health problem with around 8% of babies born prematurely, and 1.4% born very preterm (less than 32 weeks gestation) (1). Infant mortality is reported to be 144/1000 live births for infants born very preterm, compared to 1.8/1000 for those born at 38 to 41 weeks (1). Long term neurological, cognitive and attentional impairments are common and occur more frequently for very preterm births (2). These infants also face a high risk of serious neurological impairment, for example, 25% of babies born at less than 27 weeks in 2006 in England had detectable severe or moderate impairment at 3 years of age (3). Nationwide, 10% of all babies are admitted to NNU (68,000 per year in England) and around 6% of these develop one or more BSI (4). Compared with babies born at 37 weeks or more of gestation, babies born before 28 weeks have 1.6 to 2.7 times the rate of BSI, reflecting their greater immune immaturity, included immature skin and their need for more intensive care with invasive devices and intravenous feeding using parenteral nutrition (5). Very preterm babies account for a minority of admissions to NNU (10%-15% are <32 weeks of gestation) but around half of NNU care days (53%) and babies experiencing any BSI (58%) (6-8).

Based on an unpublished audit of 5 NNUs for this trial, we estimate that 8.4% of babies admitted to NNU would be born at less than 32 weeks of gestation and will require a Premicath PICC. A PICC is a very narrow tube placed through the skin and into a central vein to allow medicines, fluids or parenteral nutrition to be given into one of the large veins near to the heart. These lines can stay in place for several weeks, avoiding the need for repeated procedures, which can be harmful and distressing for small babies.

The disadvantage of a PICC is the increased risk of BSI. Bacteria or fungi stick onto the inside or around the tube and multiply. In babies with immature immunity, infection spreads via the blood stream, causing sepsis and infecting other organs. Treatment requires intravenous antibiotics for at least 5 days and sometimes antifungals are required. BSIs occur in 5-20% of babies born before 32 weeks of gestation (unpublished data from audit of 5 NNUs), mostly in association with central venous catheters. The consequences can be serious and include death, increased duration of intensive care, and in the longer term, permanent neurological impairment, even when BSI is due to less pathogenic skin organisms (9). Although intensive antibiotic treatment for BSI may be lifesaving, it also carries risks. Intensive antibiotic treatment alters the microbial ecology of the gut, which may increase the risk of necrotising enterocolitis (NEC) (10-12). NEC involves severe inflammation of the intestine and can result in necrosis of large sections of the bowel. Strategies to prevent BSI are therefore important to help babies who need a PICC avoid these serious and costly consequences (13).

There are 45 published randomised controlled trials (RCTs) of central venous catheters that have been impregnated with antiseptics or antimicrobial substances to prevent BSI, but none have been conducted in very preterm babies (14). Antibiotic impregnation was investigated in 7 RCTs and was one of the most effective interventions with an average 80% reduction in catheter-related BSI (odds ratio 0.18; 95%CI 0.08-0.34). The 7 RCTs were all confined to

adults. All used catheter-related BSI as the primary outcome, which could overestimate the effect of impregnation due to contamination of culture media with antibiotic from impregnated catheter tips. A further RCT has recently been completed of children in UK paediatric intensive care units comparing minocycline-rifampicin impregnated central venous catheters (Fr 4 or 5) with standard catheters. Heparin-bonded catheters are included as a third arm in this trial. The median duration of catheters was 2.5 days and the median age was 6 months (personal communication from trial investigators).

There is limited evidence for the effectiveness of antimicrobial impregnation in catheters inserted for weeks rather than days, or in patients receiving parenteral nutrition (15-18). Two RCTs, both in adults had median catheter durations of 44-63 days, mainly for chemotherapy (19, 20). A few patients receiving parenteral nutrition were included in these studies.

Several cost-effectiveness analyses have been published, but all focus on adult patients (21-24). A UK analysis showed that even very small reductions in absolute BSI rates would be cost-effective (as low as 0.2%) and based on results from the most relevant meta-analysis, we expect the effect size to be much larger than this (14, 21).

There are several reasons why these results in adults and children cannot be generalised to very preterm neonates. Please see section 2.2 for further details.

## **2.2 Rationale**

Antibiotic impregnated central venous catheters are used widely in paediatric and adult intensive care. However, no NNUs in the UK use AM-PICCs (despite the AM-PICCs being licensed). To address this gap, the Neonatology Clinical Studies Group of the MCRN prioritised evaluation of impregnated lines for use in preterm babies in 2012.

Reasons given by neonatologists for the lack of adoption of impregnated lines in the UK focused on the lack of RCT evidence in preterm babies and the limited availability of licensed products (AM-PICCs that are licensed and manufactured by Vygon will be used in this trial). Other reasons included concerns about antibiotic resistance and the additional costs of AM-PICCs.

A further reason for lack of uptake of AM-PICCs may be declining rates of hospital acquired BSI. In paediatric intensive care units, rates have fallen over the last decade, due in part to implementation of catheter care 'bundles' that aim to improve sterile procedures during catheter insertion and maintenance of the line (25-28). There is a paucity of evidence on trends in rates of BSI in NNU. There is therefore a clear need to take into account changing background rates of hospital acquired BSI in NNUs, through generalisability and economics analyses.

There are a large number of RCTs demonstrating benefits of impregnated lines in adults and children but no studies in very preterm neonates. However here are several reasons why results cannot be directly applied to very preterm neonates.

- i) Effects of antimicrobial impregnation may be attenuated because very preterm babies have immature immunity and skin defences, which could allow skin organisms to track internally and externally along the catheter from the insertion site (29).
- ii) Most very preterm babies with a PICC in-situ receive infusions of parenteral nutrition (a protein solution co-infused with lipid) which increase organism adherence and the development of BSI (15, 30).
- iii) The lumens of PICC used in very preterm babies are far narrower (1 Fr compared to 4 or 5 Fr used for children in the CATCH trial and 7 to 10 Fr used for adults). Narrower lumens increase bacterial adherence, potentially reducing the benefits of impregnation. Thrombosis causing obstruction of the lumen is also more common with narrower lumens.
- iv) The combination of rifampicin and an antifungal – miconazole - has not previously been evaluated in a RCT for its effect on BSI. Candidaemia is an infrequent, but well-recognised problem in very preterm neonates, and is associated with a high mortality rate (31). Use of miconazole may therefore be appropriate for this population.
- v) Emergence of resistant organisms is a major problem for NNUs. Rifampicin is known to cause emergence of resistant organisms, particularly when used as the sole antibiotic in therapeutic levels (32). However this may or may not occur with the very small dose in the AM-PICC. Rifampicin resistance may attenuate any reduction in BSI risk due to antibiotic impregnation over time. This has not been evaluated previously. Rifampicin resistance does not impact on NNU treatment regimens as this drug is not used routinely in NNUs.
- vi) Unlike more mature children, very preterm survivors of BSI are at increased risk of long-term neurological impairment, even when BSI is due to skin organisms (33). It is not known whether the reduction in BSI associated with antibiotic impregnated catheters is associated with a commensurate reduction in the risk of neurological impairment.

The trial is needed now because potential health gains are unlikely to be realised without robust evidence from a RCT. Clear evidence is needed of the effects of AM-PICC on BSI, the safety of AM-PICC, and on cost-effectiveness, before neonatologists will be willing or able to change purchasing decisions to adopt these devices in NNUs.

## 2.3 Objectives

The overall objective of the PREVAIL trial is to determine whether AM-PICCs should be introduced across the NHS for very preterm babies. To achieve this objective, we are conducting two separate but integrated analyses: Part 1: Randomised Controlled Trial and Part 2: Economic analyses.

### **2.3.1 Part I: Randomised Controlled Trial**

#### **2.3.1.1 Primary Objective**

To determine the effectiveness of antimicrobial impregnated (with rifampicin and miconazole) long lines (AM-PICC) compared with S-PICC for reducing BSI.

#### **2.3.1.2 Secondary Objectives**

**To determine the effect of AM-PICC vs S-PICC on:**

1. Rifampicin resistance in isolates from blood/CSF cultures.
2. Rifampicin resistance in isolates from PICC tips.
3. Type of organism isolated from BSI.
4. Measures of BSI (rate of BSI per 1000 PICC-days (including recurrent BSI), occurrence of 1 or more BSI, rate of catheter-related BSI per 1000 PICC days).
5. Rate of blood/CSF culture sampling per 1000 PICC days.
6. Duration of antimicrobial exposure from randomisation up to 48 hours after line removal.
7. Time to PICC removal.
8. Occurrence of Chronic Lung Disease.
9. Occurrence of necrotizing enterocolitis (NEC): Bell's stage II or III.
10. Occurrence of cranial ultrasound abnormality.
11. Requirement for treatment for retinopathy of prematurity.
12. Time to full milk feeds.
13. Duration of parenteral nutrition from randomisation until discharge home from neonatal care/death/6 months post randomisation.
14. Death:
  - a) Within six months (26 weeks) of randomisation;
  - b) Before discharge home from neonatal care.
  - c) Time to death

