### 4.2 Secondary Endpoint(s)

Outcomes captured up until 48 hours after PICC removal:

1. Rifampicin resistance in any isolate from blood/CSF culture.
2. Rifampicin resistance in any isolate from PICC tips.
3. Type of organism isolated from BSI.
4. Rate of BSI per 1000 PICC-days (including recurrent BSI).
5. Occurrence of 1 or more BSI.
6. Rate of catheter-related BSI per 1000 PICC days.
7. Rate of blood/CSF culture sampling per 1000 PICC days.
8. Duration of antimicrobial exposure from randomisation up to 48 hours after line removal.
9. Time to PICC removal.

Outcomes captured up until discharge home from neonatal care/death/6 months post randomisation:

10. Chronic lung disease 36 weeks postmenstrual age.
11. Necrotizing enterocolitis (NEC): Bell's stage II or III.
12. Treatment for retinopathy of prematurity.
13. Abnormalities on cranial ultrasound.
14. Time to full milk feeds after randomisation.
15. Total duration of parenteral nutrition from randomisation until discharge from NNU.
16. Death:
  - a) within 6 months (26 weeks) of randomisation
  - b) before discharge home from neonatal care
  - c) Time to death

For health economics outcomes, please refer to Part II: Economic Analysis.

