## **9.6 Analysis Plan**

The trial will be analysed using the International Conference on Harmonisation E9 guidelines and reported using the 'Consolidation Standard of Reporting Trials' (CONSORT) guidelines. A full and detailed statistical analysis plan will be developed prior to the final analysis of the trial. The main features of the statistical analysis plan are included here.

The analysis of primary and secondary outcomes will use the principle of intention to treat, based on all the randomised participants, as far as is practically possible. Per protocol sensitivity analyses will also be carried out on a number of outcomes, these will be specified in the statistical analysis plan. A p-value of 0.05 or less will be used to declare statistical significance for all analyses and results will be presented with 95% confidence intervals. Baseline characteristics will be presented but no comparisons will be undertaken, rather the clinical importance of any imbalance will be noted.

Kaplan-Meier survival curves and log rank tests will be used for time to event outcomes including the primary outcome 'time to first BSI'. Continuous data will be presented as means and standard deviations and analysed using two-sample tests (if data is skewed, medians and ranges will be presented and analysis will be by Mann Whitney U tests). Binary data will be reported in terms of relative risk and analysed using chi-squared or Fisher's exact tests as appropriate.

All related adverse events (AEs) and related serious adverse events (SAEs) reported by the clinical investigator will be presented, identified by treatment group, but no formal comparisons will be made across the treatment groups.

Missing data will be monitored and strategies developed to minimise its occurrence, however as much data as possible will be collected about the reasons for missing data and this will be used to inform the handling of missing data.

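### Parenteral nutrition duration stops at death and is then ranked as a plain duration, so an early death scores as a short, favourable result

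*Protocol*

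**What the plan says.** Section 2.3.1.2 lists, as a secondary objective, "Duration of parenteral nutrition from randomisation until discharge home from neonatal care/death/6 months post randomisation". The matching item in section 4.2 is worded differently: "Total duration of parenteral nutrition from randomisation until discharge from NNU". It stands under a group heading that reads "Outcomes captured up until discharge home from neonatal care/death/6 months post randomisation", so death and the 6-month limit appear there only through the heading.

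Section 9.6 fixes the analysis by type of outcome, on the intention-to-treat principle in all randomised participants as far as practicable:

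- Continuous outcomes go to two-sample tests, and "if data is skewed, medians and ranges will be presented and analysis will be by Mann Whitney U tests".
- Binary outcomes are reported as relative risks.
- Time-to-event outcomes use Kaplan-Meier curves and log-rank tests.

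Two neighbouring outcomes in section 4.2 are also exposed to death: "Chronic lung disease 36 weeks postmenstrual age" and "Time to full milk feeds after randomisation". Death is a secondary endpoint in its own right, in three forms: "within 6 months (26 weeks) of randomisation", before discharge home, and time to death.

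**The concern.** A short time on parenteral nutrition is normally read as a good sign, because the baby moved on to milk. Under the stated definition it can also mean that the baby died. A baby who dies on day 3 contributes at most 3 days and takes one of the best ranks. The definition and the test are both fixed in the protocol, so this is not a detail left to the separate statistical analysis plan; a plan that follows the protocol inherits it.

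A difference in deaths between the arms is foreseeable. Section 2.1 names death among the consequences of bloodstream infection, and the device is meant to prevent such infections. If AM-PICC lowered mortality, the nutrition comparison would move against it even with identical nutrition needs. If it raised mortality, the comparison would move in its favour.

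**Working it through.** The protocol gives no figure on this point to reproduce. The check asks which way the stated scoring moves the comparison, and by how much.

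**Inputs from the protocol.** 429 babies per arm (section 9.4). Mortality of 14.4%, from section 2.1: "Infant mortality is reported to be 144/1000 live births for infants born very preterm". That rate is per very preterm live birth. Using it for S-PICC babies in the trial is an assumption.

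**Assumptions not in the protocol.** Days on parenteral nutrition are lognormal and have the same distribution in both arms. Time to death among those who die is exponential. AM-PICC mortality is varied. Recorded duration = min(days on nutrition, days to death).

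**Direction and size.** P is the probability that a random AM-PICC baby has a longer recorded duration than a random S-PICC baby, so 0.50 means no difference. With a median of 12 days, log-SD 0.6 and mean time to death of 8 days:

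| AM-PICC mortality (S-PICC 14.4%) | P as defined | P with deaths on nutrition ranked worst |
|---|---|---|
| 14.4% | 0.50 | 0.50 |
| 10.8% | 0.51 | 0.49 |
| 7.2% | 0.52 | 0.48 |

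With 5 points more deaths on AM-PICC (19.4%), P as defined is 0.48, so that arm appears to need less nutrition.

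Ranking every death worst, including deaths after nutrition had stopped, is a different rule. It gives 0.5 − (mortality difference)/2: 0.5 − 0.036/2 = 0.482 and 0.5 − 0.072/2 = 0.464.

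**Sensitivity to timing.** With mean time to death of 30 days, P as defined is 0.505 (10.8%) or 0.509 (7.2%). With 60 days it is 0.503 or 0.505.

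**Against sampling error.** SE of P = √[(2×429 + 1)/(12×429²)] = √(859/2,208,492) = 0.020. The unrounded values 0.5114 and 0.5240 lie 0.0114/0.0197 ≈ 0.6 and 0.0240/0.0197 ≈ 1.2 standard errors from 0.50.

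**Effect on the test.** In 1,000 simulated trials per scenario (median 14 days, log-SD 0.7, mean time to death 14 days, no device effect on nutrition), Mann-Whitney was significant in favour of AM-PICC as follows:

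- Equal mortality: 3.2% of trials (nominal 2.5%).
- 5 points more AM-PICC deaths: 8.9% (mean 16.1 against 16.6 days).
- 10 points more AM-PICC deaths: 23.4% (mean 15.7 against 16.6 days).

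**Chronic lung disease.** If deaths before 36 weeks were coded as non-cases, and survivors had equal risk, RR = (1 − m_AM)/(1 − m_S): 0.892/0.856 = 1.04 or 0.928/0.856 = 1.08. In survivors RR = 1.00. For death or chronic lung disease, RR = [m_AM + (1 − m_AM)c]/[m_S + (1 − m_S)c]. With an assumed survivor risk c of 0.3 to 0.5, this gives 0.94 to 0.97 (10.8%) or 0.87 to 0.94 (7.2%).

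**Time to full feeds.** The same trials with excess AM-PICC deaths gave a mean log-rank Z of about 0.02 when deaths were censored. When deaths were kept at risk as never fed, mean Z was −1.1 (5 points more) and −2.1 (10 points more), against the arm with more deaths.

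**The case against.** The case against has several parts, and most of it narrows the point without removing it.

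- **The shift is small.** It is about one standard error or less in most scenarios and shrinks if deaths come later. This stands.
- **The mortality scenarios are generous.** The design expects infection to fall from 14% to 7%. A fall in mortality from 14.4% to 7.2% would prevent more deaths (7.2 points) than infections (7 points), and the 3.6-point fall would need about half of the prevented infections to have been fatal. This stands; the scenarios show direction, not an expected size.
- **Ranking deaths worst puts mortality into the score.** It does, so the reversal of direction is not a recovered effect on nutrition. The components must be shown.
- **Death is reported separately.** A reader would see excess deaths beside the nutrition result, so the outcome would not conceal harm. Separate reporting limits the damage but does not correct the nutrition test.

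A reader might also infer that all three outcomes reward early death. The protocol does not support that. It nowhere says that a baby who dies before 36 weeks counts as free of chronic lung disease; the denominator may be settled in the separate analysis plan. For time to full feeds, a death is either censored, which is neutral if independent of feeding, or never fed, which is unfavourable. Neither is a good result. Nor is 144 per 1,000 a mortality figure for this trial: enrolled babies need a 1 Fr line, usually placed after the first 2 days, and the protocol gives no rate for them.

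**Conclusion.** The point holds for duration of parenteral nutrition. It rests on two statements in the protocol: the count ends at death, and the result is compared as an ordinary continuous outcome. Together they favour the arm with more early deaths whenever mortality differs. The size is modest: P of about 0.51 or 0.52 instead of 0.50 under the assumed mortality gaps and a mean of 8 days to death, closer to 0.50 with later deaths, and no shift with equal mortality.

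For chronic lung disease, the sound statement is only that it cannot be observed in babies who die before 36 weeks. A relative risk of 1.04 or 1.08 applies solely if deaths are coded as non-cases. Time to full feeds is not affected in this way. The primary outcome and the sample size are untouched. It is worth correcting because it is cheap.

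**What to change.** In section 9.6:

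1. State that babies who die while still on parenteral nutrition take the worst rank in the Mann-Whitney comparison. Show the durations among survivors and the number of deaths in each arm beside it.
2. Reconcile the end of the count between section 2.3.1.2 (discharge home, death or 6 months) and the item in section 4.2 (discharge from the unit).
3. Report death or chronic lung disease at 36 weeks, with each component shown, beside chronic lung disease alone.
4. Optionally, add a cumulative incidence curve for full milk feeds with death as a competing event.

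The cost is wording. Section 6.6 already has details of death and duration of parenteral nutrition recorded on Form 7a, and time to death is an endpoint. The form is not shown, so confirm that it identifies babies still on parenteral nutrition at death. The sample size does not change. The downside is that the ranked score mixes mortality with nutrition and must not be reported without its components.
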